## **X. Effectiveness Analyses**

### **A. Primary Effectiveness**

The data from all study sites or pseudo-sites will be pooled and the primary analysis will be done by a one-sided exact binomial test of the performance goal for PPV and NPV with nominal P-value of 0.025. Alternatively, the lower one-sided 97.5% confidence limit for PPV and NPV will be computed and compared to each performance goal. If these limits both are greater than the performance goal, then the null hypothesis will be rejected.

An exploratory descriptive analysis will be provided for PPV and NPV by study site or pseudo-site. The point estimates and 95% two-sided confidence limits will be presented by study site or pseudo-site. Recall that because no site was intended to have adequate power for the primary endpoint, this analysis is unlikely to show that by-site lower confidence limit for PPV and NPV will be above the performance goals.

### **B. Secondary Effectiveness**

The first secondary endpoints, co-secondary endpoints of sensitivity and specificity of the ProLung Test will be estimated. Sensitivity is defined as the proportion of subjects with ProLung Tests that are positive among subjects with positive biopsy results. Specificity is defined as the proportion of subjects with ProLung tests that are negative among the subjects with a negative biopsy or CT follow-up result. Each of these endpoints will be estimated from the data and presented with their 95% exact confidence intervals.

The second secondary endpoint the test of the sum of PPV and NPV will be tested with a continuity corrected z-statistic presented below. An estimate is needed for the standard error of the sum of PPV and NPV, because PPV and NPV are unlikely to have equal variances, the standard error of the sum can be estimated by the following expression for linear combinations of items that have unequal variances.

$$SE(PPV + NPV) = \sqrt{\frac{PPV(1-PPV)}{TP+FP} + \frac{NPV(1-NPV)}{TN+FN} + \rho \sqrt{\frac{PPV(1-PPV)}{TP+FP}} \sqrt{\frac{NPV(1-NPV)}{TN+FN}}}$$

where TP is the number of true positives, FP is the number of false positives, TN is the number of true negatives, FN is the number of false negatives, and  $\rho$  is the estimate of the correlation coefficient between PPV and NPV. Note that the PPV has a negative correlation with NPV so  $\rho$  is negative reducing the standard error than if PPV and NPV were independent.

The test statistic is given by the formula below.

$$Z = \frac{(PPV+NPV - \frac{1}{2}(\frac{1}{TP+FP} + \frac{1}{TN+FN}) - 1)}{SE(PPV+NPV)}$$

If  $Z > 1.96$  ( $P < 0.025$ ), then the sum of PPV and NPV will be considered to be greater than unity. Alternatively, if the lower one-sided 97.5% confidence limit of the sum is greater than 1, the null hypothesis will be rejected. The lower confidence limit is computed by the formula below:

$$LCL_{0.975} = (PPV + NPV) - 1.96 * SE(PPV + NPV).$$

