### 1. Performance Goal Derivation and Sample Size

From the algorithm development data, the observed rate for  $PPV = 0.861$ , and for  $NPV = 0.471$ . Note that this PPV and NPV estimate are based on a prevalence of 0.74 from the algorithm development cohort. Since the prevalence of the validation cohort has a lower prevalence (approximately 0.637), the PPV will be lower and the NPV will be higher. The estimate for PPV is 0.778 and for NPV is 0.551. The performance goals will be computed based on these estimates of PPV and NPV.

Recall that the denominator of the PPV is the number of total tests that were deemed positive from the ProLung Test. Likewise, the NPV computation uses as its denominator the total number of ProLung Tests that turned out negative. In the 200 patients used in the algorithm study, there are 148 positive patients and 52 negative patients 109/200 (54.5%) were true positives (TP), 39/200 (19.5%) were false negatives (FN), 16/200 (8.0%) were false positives (FP), and 36/200 (18.0%) were true negatives (TN). In the validation study, there are 111 patients with malignant lesions and 63 patients with benign lesions. The performance goals are computed below that are achievable with this distribution of positive and negative patients.

Statistical simulation was performed to determine the power and estimates of PPV and NPV for the validation cohort. From that simulation an average  $PPV = 0.778$  and  $NPV = 0.552$ . This results in the following estimates: 78 TP, 33 FN, 22 FP, and 41 TN cases. The number of positive test results are  $TP + FP = 100$ , and the total number of negative test results is  $FN + TN = 74$ . To achieve approximately 90% power for PPV with 111 positive test results and a point estimate of 0.778 will require  $PG_{Pos} = 0.638$ . To achieve about 90% power for NPV with the 63 negative test results and a point estimate for NPV of 0.551, the  $PG_{Neg} = 0.381$ . Note that 90% power is required because the coprimary status indicates that both tests must be achieved so the power of the joint hypothesis is  $0.90 * 0.90 = 0.81$ , the usual power required for the tests. The power for the sum of PPV and NPV from the 10-simulation averaged 0.99.

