## **VI. Multiplicity**

There are two coprimary hypothesis to be tested in this study, the descriptive analysis of the secondary endpoints using statistical estimation to provide exact 95% confidence limits for sensitivity and specificity, and the hypothesis test of the sum of PPV and NPV will preserve the nominal alpha level. Using the hierarchical closed form method to control alpha inflation, allows the descriptive presentation for the co-secondary endpoints of sensitivity and specificity and can use the nominal study alpha to present two-sided 95% confidence limits and the hypothesis test of the sum at the nominal alpha level as long as both co-primary hypothesis test results in statistical significance. The coprimary endpoints must both be statistically significant so there is no alpha inflation for the two coprimary hypothesis tests.

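### The standard error of PPV+NPV carries a negative correlation term that should not be there, so the lower confidence limit for the sum is too high; no gated decision changes.

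*SAP*

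**What the plan says.** SAP section X.B (Secondary Effectiveness) takes the variance of PPV+NPV as the two binomial variances plus ρ times the product of the two standard errors. It says that ρ "is the estimate of the correlation coefficient between PPV and NPV", and then: "Note that the PPV has a negative correlation with NPV so" ρ "is negative reducing the standard error than if PPV and NPV were independent". No value or method of estimation for ρ follows.

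Two decision rules use this standard error. If the continuity-corrected Z exceeds 1.96, "then the sum of PPV and NPV will be considered to be greater than unity". The second rule reads: "Alternatively, if the lower one-sided 97.5% confidence limit of the sum is greater than 1, the null hypothesis will be rejected". The formula for that limit has no continuity correction.

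Two other sections matter. Section V.A.1 fixes the denominators: "Recall that the denominator of the PPV is the number of total tests that were deemed positive from the ProLung Test", while "the NPV computation uses as its denominator the total number of ProLung Tests that turned out negative". Section VI (Multiplicity) allows the test of the sum at the nominal level only "as long as both co-primary hypothesis test results in statistical significance".

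**The concern.** No subject is in both denominators. A negative correlation between the two estimates therefore has no evident source, yet the SAP relies on one to reduce the standard error. A standard error that is too small gives a lower limit that is too high and covers the true sum less often than stated.

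The input is also undefined. One 2×2 table yields one PPV and one NPV, so it offers no obvious sample correlation to compute. The analyst would have to choose ρ, and the SAP's only instruction is its sign.

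Two smaller faults sit in the same formulas. The cross term lacks the factor 2 of the usual variance of a sum. And the two rules offered as alternatives do not agree, because only Z subtracts a continuity correction.

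**Working it through.** **Inputs.** From SAP V.A.1: expected table TP 78, FN 33, FP 22, TN 41 (100 positive and 74 negative tests); 111 malignant and 63 benign, N = 174; performance goals 0.638 for PPV and 0.381 for NPV; stated power for the sum 0.99. From SAP X.A: one-sided exact binomial co-primary tests at 0.025. From SAP X.B: the formulas for SE, Z and the limit. All non-zero values of ρ below are assumptions.

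**Stated power.** I simulated 1,000,000 tables per sampling scheme with sensitivity 78/111 and specificity 41/63, using the SAP's Z > 1.96 with ρ = 0. Power is 0.993 to 0.994, which agrees with the stated 0.99. That figure therefore does not need a negative ρ.

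**Is the correlation negative?** The same simulations give:

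- Cohort (multinomial) sampling: correlation 0.00, SD of the sum 0.071.
- Test totals fixed at 100 and 74: correlation 0.00, SD of the sum 0.071.
- Diagnosis totals fixed at 111 and 63: correlation +0.78, SD of the sum 0.0705.

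No scheme gives a negative value. In the third, the separate variances are smaller than the binomial ones (SDs 0.0315 and 0.0431), and this offsets the positive covariance. The mean ρ = 0 standard error there is 0.0710, so it is still right for the sum.

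**Standard error on the expected table.**

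- PPV = 78/100 = 0.780; s₁² = 0.78 × 0.22 / 100 = 0.001716; s₁ = 0.0414.
- NPV = 41/74 = 0.554; s₂² = 0.554 × 0.446 / 74 = 0.003339; s₂ = 0.0578.
- Sum = 1.334; s₁s₂ = 0.002394.
- At ρ = 0: SE = √(0.001716 + 0.003339) = 0.0711, which equals the exact SD of the sum given 100 positive and 74 negative tests.
- At ρ = −0.5: SE = √(0.005055 − 0.001197) = 0.0621.

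The limit is 1.334 − 1.96 × SE. Coverage is exact, by enumerating independent Binomial(100, 0.78) and Binomial(74, 41/74) counts.

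| ρ (assumed) | SE | SE too small by | Lower limit | Coverage (nominal 0.975) |
|---|---|---|---|---|
| 0 | 0.0711 | – | 1.195 | 0.970 |
| −0.1 | 0.0694 | 2% | 1.198 | 0.967 |
| −0.3 | 0.0659 | 7% | 1.205 | 0.959 |
| −0.5 | 0.0621 | 13% | 1.212 | 0.950 |
| −0.9 | 0.0539 | 24% | 1.228 | 0.926 |

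**The factor 2.** With negative ρ, adding it shrinks the standard error further: at ρ = −0.5, √(0.005055 − 0.002394) = 0.0516 instead of 0.0621. It would make the error worse.

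**The continuity correction.** It equals ½(1/100 + 1/74) = 0.0118. At ρ = 0, subtracting it from the limit as well gives 1.195 − 0.012 = 1.183, with coverage 0.979.

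**Rejection rate outside the gate.** For an uninformative test (probability of a positive result 100/174 in both disease groups), at ρ = 0, −0.1, −0.3, −0.5 and −0.9:

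- Limit rule: 0.025–0.026, then about 0.029, 0.035, 0.045 and 0.071.
- Z rule: about 0.018, 0.020, 0.025, 0.031 and 0.053.

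The SAP does not run the test this way; the figures show only what the term does on its own.

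**Rejection behind the gate.** I enumerated every table with N = 174 in which both exact co-primary tests succeed. There are 109,852 of them (109,642 if restricted to 5–169 positive tests and a non-zero SE). All reject at ρ = 0: the smallest Z is 2.73 and the smallest limit 1.095. A negative ρ only makes rejection easier, so it cannot change any of these decisions. The reason is simple: the two goals already add to 0.638 + 0.381 = 1.019.

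**The case against.** The best case for leaving this as a minor note has four parts.

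- **No decision depends on it.** The gate and the two goals settle the sum test before the standard error matters. This stands.
- **The size is unknown.** The SAP gives no ρ, and at −0.1 the limit moves only from 1.195 to 1.198. The larger effects need values for which the documents give no basis. This also stands, but it is partly the complaint itself: a prespecified formula should not leave its result to an undefined input.
- **The SAP names the limit as a decision rule and does not expressly promise to report it.** That is correct. But the limit is prespecified for a named secondary endpoint, and it is the only interval the SAP defines for the sum, so it is likely to be shown.
- **Zero covariance is not universal.** With diagnosis totals held fixed the correlation is +0.78. That is right, but it gives no support to a negative ρ, and the ρ = 0 standard error of the sum remains correct in that case too.

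The continuity correction is partly a matter of preference: coverage of 0.970 without it and 0.979 with it are about equally far from 0.975. The need to treat Z and the limit alike is not.

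**Conclusion.** The concern holds. The statement that PPV and NPV are negatively correlated is wrong for these estimates, and the ρ = 0 standard error is right under each of the three sampling schemes examined. Any negative ρ makes the lower limit for the sum too high: by 0.003 at ρ = −0.1 and 0.034 at ρ = −0.9 on the expected table, with one-sided coverage of 0.967 and 0.926. These sizes rest on the SAP's expected table and on assumed values of ρ. That no gated decision changes rests on the goals of 0.638 and 0.381, the one-sided 0.025 level and N = 174. The matter should be fixed, but its reach is one secondary limit.

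**What to change.** In SAP section X.B, delete the ρ term, its definition and the sentence on negative correlation, leaving

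SE = √[PPV(1 − PPV)/(TP + FP) + NPV(1 − NPV)/(TN + FN)].

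Do not repair the term by adding the factor 2.

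Use the same continuity correction in both rules. Applying it in both gives

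LCL = (PPV + NPV) − ½[1/(TP + FP) + 1/(TN + FN)] − 1.96 × SE,

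so that the limit exceeds 1 exactly when Z exceeds 1.96. This also puts coverage at the planned values slightly above nominal (0.979) instead of slightly below (0.970).

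The cost is SAP wording. On the expected table the limit becomes 1.195, or 1.183 with the correction. Power of the Z rule at ρ = 0 stays at 0.993 to 0.994, and no decision behind the gate changes.

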### C. Additional Effectiveness Endpoint Analyses - **Subgroup Analyses of Sensitivity and Specificity**

Descriptive presentation of sensitivity and specificity by selected subgroups will be presented. The subgroup variables and segments are presented below.

Age (<50, 50 to 59, 60-69, and  $\geq 70$ )

Gender (Male and Female)

BMI (<20, 20-25, 26-30,  $\geq 30$ ).

## XI. **Safety Analyses**

The adverse events in this study will be displayed descriptively. The number of subjects with at least one event, the total number of subjects evaluated, the percentage, the 95% confidence limits on the percentage, and the total number of events of a given type are to be presented.

## XII. **Scan Eligibility for Analysis**

ProLung Tests are excluded from analysis for quality test issues which may include missing patient measurement points, instances when the operator did not follow device training protocol, and other quality issues. The duration of the scan more than 40 minutes will not be an exclusion factor.

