4.3.2 Events Eliminating Subjects from Primary Analyses

- Incomplete or lost medical records.
- Inconclusive biopsy result.
- Incomplete ProLung Test data.

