### **B. Completed Cases (CC) Population**

All subjects that have paired results of both ProLung Test and either confirmatory tissue biopsy (of cancer or benign condition) or radiologic stability to infer a benign diagnosis.. The primary and secondary analyses require paired evaluations and therefore will be conducted in the completed cases population.

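### SAP XII lets ProLung Tests be excluded on open-ended quality grounds, and nothing requires the decision to be blinded or locked before results meet diagnoses; in a near-miss, one to three exclusions can reverse a co-primary test.

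*SAP*

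**What the plan says.** SAP XII states that "ProLung Tests are excluded from analysis for quality test issues which may include missing patient measurement points", and extends this to "instances when the operator did not follow device training protocol, and other quality issues". The grounds are given as examples and end in a catch-all. The only firm limit is that a scan lasting more than 40 minutes is not excluded for its length. The section names no threshold, decision-maker, timing, log or blinding.

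Protocol 4.3.2 lists what removes a subject from the primary analyses. Its one test-related entry is "Incomplete ProLung Test data".

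SAP IV.B defines the completed-cases population, used for the primary analysis, as "All subjects that have paired results of both ProLung Test and either confirmatory tissue biopsy" or radiologic stability. It does not refer to SAP XII.

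Protocol 3.2 blinds the Sponsor's Statistician to diagnosis until recruitment and monitoring end. It blinds the site team, including operators, to the algorithm result, while leaving diagnoses open to that team. Test results go to the sponsor, the statistician or both. Under protocol 7.1 a sponsor monitor checks every CRF against source and the sponsor collects the originals. Under protocol 5.10 diagnostic outcomes are recorded on CRF pages.

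SAP V.A.1 says of the validation cohort that "there are 111 patients with malignant lesions and 63 patients with benign lesions".

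SAP X.A tests each co-primary with a "one-sided exact binomial test of the performance goal for PPV and NPV with nominal P-value of 0.025". SAP VI adds: "The coprimary endpoints must both be statistically significant".

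**The concern.** PPV and NPV are proportions among tests that returned a result. Removing a false positive shrinks the PPV denominator and leaves its numerator alone; removing a false negative does the same for NPV. A rule for dropping scans therefore acts directly on both co-primary endpoints. Such a rule is harmless to the type I error if it is applied without knowing which scans were wrong. It is not harmless if the person applying it can see both the test result and the diagnosis.

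Missing measurement points fit the protocol's ground. Operator deviation and unspecified quality problems go further and call for judgement. The sponsor, as an organisation, may receive the test results and collects the CRFs that carry diagnoses. The operators, who would know of a training deviation, sit in a team with access to diagnoses. Neither document ties scan eligibility to the protocol 3.2 blind or requires it to be settled before the blind is broken.

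**Working it through.** **Inputs.** Performance goals 0.638 (PPV) and 0.381 (NPV), and the expected table of 78 TP, 22 FP, 33 FN and 41 TN, come from SAP V.A.1. The exact one-sided test at 0.025 comes from SAP X.A.

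**Formula.** For x correct results among n tests, p = P(X ≥ x), with X ~ Binomial(n, goal). The test passes if p ≤ 0.025, which matches a Clopper-Pearson lower 97.5% limit above the goal.

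**The SAP's own table first.** Positive tests: 78 + 22 = 100. Negative tests: 33 + 41 = 74.
- PPV 78/100: p = 0.0016, lower limit 0.686 against 0.638. Pass.
- NPV 41/74: p = 0.0019, lower limit 0.434 against 0.381. Pass.

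The smallest passing counts are 74/100 (p = 0.0199) and 37/74 (p = 0.0246).

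**Near-misses, removing wrong-result scans one at a time.**

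| Test | Removed | Count | p | Lower limit | Result |
|---|---|---|---|---|---|
| PPV | none | 73/100 | 0.0331 | 0.632 | fail |
| PPV | 1 FP | 73/99 | 0.0235 | 0.6393 | pass |
| PPV | none | 72/100 | 0.0526 | 0.621 | fail |
| PPV | 2 FP | 72/98 | 0.0276 | 0.636 | fail |
| PPV | 3 FP | 72/97 | 0.0192 | 0.6435 | pass |
| NPV | none | 36/74 | 0.0415 | 0.3685 | fail |
| NPV | 2 FN | 36/72 | 0.0263 | 0.380 | fail |
| NPV | 3 FN | 36/71 | 0.0206 | 0.3856 | pass |

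**Type I error.** If up to three wrong-result scans could be removed with outcomes known, the test would in effect pass from 72/100 and from 36/74. The error rate at the goal would rise from 0.0199 to 0.0526 for PPV and from 0.0246 to 0.0415 for NPV.

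**How likely is a near-miss?** At the SAP's planning values (PPV 0.778, NPV 0.551) and these denominators:
- PPV: power is 0.849 with no removals and 0.932 with up to three. The difference, 0.083, is the chance of 72 or 73 out of 100. As a share of failures it is 0.083 / (1 − 0.849) = 55%.
- NPV: 0.891 − 0.841 = 0.050 is the chance of exactly 36/74. As a share of failures it is 0.050 / (1 − 0.841) = 31%.

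**Sensitivity to the denominator.** The SAP's power statement uses other counts, as in "To achieve about 90% power for NPV with the 63 negative test results and a point estimate for NPV of 0.551", with 111 for PPV. Those equal its malignant and benign totals. With them the picture is similar: 80/111 (p = 0.0413) passes after two removals (80/109, p = 0.0218), and 31/63 (p = 0.0473) passes after three (31/60, p = 0.0223). The stated power of about 90% for each test is not fully reproduced with either set: exact power is 0.866 (n = 111) and 0.713 (n = 63), or 0.849 (n = 100) and 0.841 (n = 74). That is a separate matter and the point here does not depend on it.

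**The case against.** **The blind already splits the information.** Selecting wrong results requires both the test result and the diagnosis, and protocol 3.2 keeps one from the statistician and the other from the sites. This stands as partial protection. It would be enough if the blinded statistician settled eligibility before unblinding, but neither document says so, and other sponsor staff are not stated to be blind to diagnosis.

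**SAP XII may only define a usable scan.** A reader might infer that it contradicts SAP IV.B. The documents do not support that: an excluded scan can reasonably be read as leaving no paired result. Nor is protocol 4.3.2 worded as exhaustive; protocol 8.1 adds a further restriction, on biopsy timing. What stands is that SAP XII is broader than the only test-related ground in 4.3.2 and that the two are not reconciled.

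**The worst-case analysis in SAP IX would expose the problem.** It scores a missing test as negative where cancer is present and positive where it is not, so a dropped false negative or false positive returns to its own cell. That is a real safeguard if excluded scans count as missing. SAP IX does not say that they do, and a sensitivity analysis does not decide the primary result.

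**The reversal is a boundary case.** This stands. The result must be just short, every removed scan must come from one wrong-result cell, and the other co-primary must pass too. If both failed at 72/100 and 36/74, six targeted removals would be needed.

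**Conclusion.** The gap is real, and it is one of safeguards. SAP XII permits exclusions on open-ended grounds wider than protocol 4.3.2, and no text requires them to be decided blind or locked before test results are linked to diagnoses. In a near-miss, one to three removals from a single wrong-result cell reverse PPV, and three reverse NPV. At the SAP's planning values the reachable near-misses have a probability of about 8% (PPV) and 5% (NPV). These figures assume 100 positive and 74 negative tests and removal with outcomes known; at the expected table nothing needs rescuing.

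Stronger conclusions are tempting and are not supported:
- A reader might infer from the diagnosis totals in SAP V.A.1 that outcomes had been linked to test results when the rule was written. Those totals are margins only, and the SAP presents its 2x2 table as simulated estimates.
- A reader might treat three scans out of 174 as the operative scenario. The documents do not say whether the 174 are counted before or after scan exclusions.
- A reader might infer that even blinded exclusion inflates performance. That assumes scans with operator deviations perform worse, and no figure in the documents shows it.

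A change before the analysis is warranted, because the protection is cheap and both co-primaries depend on it.

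**What to change.** In SAP XII:

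1. Replace the illustrative wording and the catch-all with a closed list of objective criteria, reconciled with protocol 4.3.2. Excluding technically invalid tests under such criteria is defensible, so the primary analysis need not be limited to incomplete data alone.
2. Have existing staff without access to diagnosis or test result decide each exclusion from the measurement file and the operator record. Lock the list before test results are linked to diagnoses.
3. Repeat the PPV and NPV analyses with every scan on which the locked algorithm returns a result. List each exclusion with its reason and its 2x2 cell, and state that excluded scans enter the worst-case analysis in SAP IX.
4. State whether the 174 subjects are counted before or after scan exclusions.

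The cost is SAP wording, a blinded review by existing staff and a little more analysis. No new patients or data are needed. The downside is that the all-scans estimates may be slightly less favourable.
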